2.6.4 End of Treatment Safety Follow-up Visit

All patients receiving at least one dose of HBI-8000 and discontinuing treatment for any reason except death will be assessed 30 (\pm 3) days after the last dosing of study drug, before the initiation of new cancer treatment or before the initiation of administration of commercial product of HBI-8000, whichever is earlier. Any patient for whom study treatment has been discontinued should complete study procedures listed in the EoT visit. At EoT safety visit, evaluations will include physical examination, vital signs, body weight, ECOG performance

status, hematology, blood chemistry, urinalysis, pregnancy test (if applicable), ECG, and assessment of any ongoing adverse events. If a patient discontinues study treatment before PD is recorded, and if the last tumor assessment was >30 days earlier from the EoT visit, tumor assessment should be performed at EoT. In these patients, further tumor assessments are to be performed approximately every 3 months \pm 2 weeks until PD or the start of new cancer therapy whichever occurs first, unless consent to study participation is withdrawn or by completion of the whole study. If subjects cannot visit at site for this examination due to COVID-19 situation, investigators can skip the examination, and the assessment is to be performed approximately every 6 months \pm 2 weeks. In this case, the investigator should document that fact in the medical record.

Patients with HBI-8000-related AEs of Grade ≥ 2 observed at the EoT visit should be followed-up and assessed monthly (phone calls/clinic visits) until the AEs have resolved to Grade ≤ 1 or are determined to be chronic, or patient receives other anti-cancer therapy.

2.6.5 Survival Follow-up

Follow-up for survival (and tumor status in patients in whom PD has not yet been observed) should occur at approximately 3-month intervals after the EoT visit. Survival status may be conducted every 3 months \pm 2 weeks by telephone contact or e-mail until death or end of study, defined as timing that the last Japanese subject initiates administration of the commercial product of HBI-8000. If there is no subject who is receiving study treatment at the time of the PTCL approval in Japan, the whole study will be completed at the time of the approval. The first subsequent anticancer therapy during this survival follow up period should be recorded with regimen and start date in the appropriate Electronic Case Report Form (eCRF).

2.6.6 Patient Withdrawal

Patients have the right to withdraw from the study at any time for any reason, and the investigator should try to ascertain the reason for withdrawal as completely as possible. The investigator also has the authority to determine whether a patient should be discontinued from the study. Study treatment may be discontinued and the patient withdrawn from the study under the following circumstances:

- Unacceptable toxicity (AE)
- Progression of the disease under study, except for isolated progression in skin lesion
- Decision by the investigator to permanently discontinue study drug administration
- Intercurrent illness that would, in the judgment of the investigator, affect clinical assessments, patient safety, or follow-up significantly
- Significant protocol deviations that jeopardize the usefulness of the data
- Repeated patient noncompliance
- Patient is beginning another anti-cancer treatment protocol
- Patient becomes pregnant
- Patient requests to withdraw informed consent
- Study termination by the sponsor

All patients who withdraw from study treatment must complete an EoT visit, to be performed 30 ± 3 days after the last dosing of the study drug (see Section 9.1), before the initiation of new cancer treatment or before the initiation of administration of commercial product of HBI-8000, whichever is earlier. A patient may withdraw consent for treatment but still allow follow-up, in which case he/she should be followed for safety, survival, and disease status. If a patient has withdrawn consent to study participation entirely, no subsequent follow-up will be performed.

Patients who are lost to follow up or withdraw consent for study participation prior to receiving HBI-8000 or who withdraw before completing Cycle 1 for reasons unrelated to drug AEs or PD will be replaced.

2.6.7 Discontinuation of the Study

The whole study will be discontinued in any of the following cases:

- Sponsor decides to discontinue development of the compound or the study
- In the event of sponsor or regulatory authorities obtain safety information which does not allow continuation of the study

2.6.8 Management and Dosage Modifications for Unacceptable Hematologic and Non-Hematologic Adverse Events

National Cancer Institute Common Terminology Criteria for Adverse Events (NCI CTCAE) version 4.03 will be used to grade the severity of toxicities. An unacceptable toxicity is defined as the following treatment-related AEs:

- Grade 4 afebrile neutropenia >7 days despite optimal growth factor support
- Grade ≥ 3 febrile neutropenia or neutropenic infection
- Grade ≥ 3 thrombocytopenia with clinically significant bleeding or Grade ≥ 3 thrombocytopenia requiring a platelet transfusion
- Grade ≥ 3 nausea, vomiting, diarrhea, or electrolyte imbalances lasting greater than 48 hours despite optimal prophylactic and curative treatment
- Grade ≥ 3 allergic reaction
- Grade ≥ 3 other non-hematologic AEs
- Treatment delay >14 days secondary to recovery from study drugs- related AEs

Table 1 summarizes the guidelines for dosage adjustment in the event of unacceptable AEs. Two dose reductions are allowed (from 40 mg to 30mg, or from 30 mg to 20 mg). If unacceptable AEs recur despite 2 dose reductions, the study treatment will be permanently discontinued and post-treatment follow-up ensues. However, if the patients are having clinical benefit, further treatment may be considered after discussion with the sponsor. In the event of AE, such as hematological AE-uncomplicated, necessitating two treatment interruptions, dose will be reduced when treatment resumes. However, if strongly needed for patient safety, dose can be reduced according to the investigator judgement, even if unacceptable hematological AE-uncomplicated is occurred once.

Table 1: HBI-8000 Tablet Dosage Adjustment Guidelines

AE Category	AE Description	Dosage interruption with/without Reduction
Hematological Adverse Events--Uncomplicated	
• Neutropenia Grade 3 or 4 upon observation• Thrombocytopenia Grade 3 or 4 upon observation	Hold dose, Initiate G-CSF, once resolved to ≤ 1 within 2 weeks, resume at same dose Hold dose, once resolved to ≤ 1 within 2 weeks, resume at same dose. If recovery takes >2 weeks, discontinue study drug.
Hematological Adverse Events--Complicated	
• Grade 4 afebrile neutropenia >7 days despite optimal growth factor support• Grade ≥ 3 febrile neutropenia or neutropenic infection• Grade ≥ 3 thrombocytopenia with clinically significant bleeding or Grade ≥ 3 thrombocytopenia requiring a platelet transfusion	Hold doses, once resolved to ≤ 1 within 2 weeks, resume at reduced dose (from 40 mg to 30 mg, or from 30 mg to 20 mg); If recovery takes >2 weeks, discontinue study drug.
Non-Hematological Adverse Events (excluding laboratory values without clinical significance)	Grade 3	Hold doses, once resolved to ≤ 1 within 2 weeks, resume at reduced dose (from 40 mg to 30 mg, or from 30 mg to 20 mg) with appropriate prophylaxis as applicable. If recovery takes >2 weeks, discontinue study drug.
	Grade 4	Discontinue study drug

AE: Adverse Event; G-CSF: granulocyte colony stimulating factor

G-CSF is recommended to be prescribed when uncomplicated grade 3 or 4 neutropenia is observed. Patient management should follow institution guidelines and be recorded in eCRFs. Laboratory tests should be obtained at least once a week to monitor recovery.

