Study Design:	
This is a Phase 2b, open-label, non-randomized, single arm study to evaluate the safety, efficacy, and PK of HBI-8000 40 mg BIW in patients with relapsed or refractory PTCL (R/R PTCL). HBI-8000 will be administered orally approximately 30 minutes after any regular meal. The treatment will be continuous, with 3-4 days between dosing. A cycle is defined as 28 days solely for the purpose to schedule assessments required by the study.
 
The study will continue till the last active Japanese subject initiates administration of the commercial product of HBI-8000 after the marketing authorization approval for relapsed or refractory PTCL in Japan. If there is no subject who is receiving study treatment at the time of the PTCL approval in Japan, the whole study will be completed at the time of the approval.
 
In Japan, “Phase 2 study” shall be read as “post-marketing clinical study” and “investigator” shall be read as “post-marketing clinical study investigator” in this protocol after the marketing approval. In addition, other related terms are to be replaced in accordance with Article 56 of the Ministerial Ordinance on the Standards for the Implementation of Clinical Studies on Pharmaceutical Product (Japan GCP).
 
Treatment-related adverse events (AEs) will be graded according to National Cancer Institute Common Terminology Criteria for Adverse Events (NCI CTCAE) version 4.03. In the event of unacceptable toxicities, study drug will be held until recovery and dosing will be resumed at reduced dose level, following protocol guidelines. An unacceptable toxicity is defined as the following:
	

- Grade 4 afebrile neutropenia > 7 days despite optimal growth factor support
- Grade ≥ 3 febrile neutropenia or neutropenic infection
- Grade ≥ 3 thrombocytopenia with clinically significant bleeding or Grade ≥ 3 thrombocytopenia requiring a platelet transfusion
- Grade ≥ 3 nausea, vomiting, diarrhea, or electrolyte imbalances lasting greater than 48 hours despite optimal prophylactic and curative treatment
- Grade ≥ 3 allergic reaction
- Grade ≥ 3 other non-hematologic AEs
- Treatment delay >14 days secondary to recovery from study drugs- related AEs

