2.4.1 Safety Determination and Criteria for Dose Modification or Interruption

National Cancer Institute Common Terminology Criteria for Adverse Events (NCI-CTCAE) version 4.03 will be used to grade the severity of toxicities. Abnormalities of laboratory tests (investigation) must be evaluated for clinical significance. Study treatment may be held, and dose may be reduced in the event of unacceptable toxicities. (see Section 2.6.8 for Guidelines.)

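### For the same adverse events, the synopsis resumes dosing after a recovery delay of more than 14 days and Table 1 stops it; the two must be reconciled

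*Combined protocol and SAP*

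**What the plan says.** All the text below is current version 6.0 wording, not amendment history.

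- **Synopsis, Study Design.** "In the event of unacceptable toxicities, study drug will be held until recovery and dosing will be resumed at reduced dose level, following protocol guidelines". The list that follows defines unacceptable toxicity, and its last item is "Treatment delay >14 days secondary to recovery from study drugs- related AEs".
- **Section 2.4.1.** This is permissive: "Study treatment may be held, and dose may be reduced in the event of unacceptable toxicities". It refers to Section 2.6.8.
- **Section 2.6.6.** Unacceptable toxicity is one of the circumstances introduced by "Study treatment may be discontinued and the patient withdrawn from the study under the following circumstances".
- **Section 2.6.8, text.** The list is repeated, including the delay item, and then: "Table 1 summarizes the guidelines for dosage adjustment in the event of unacceptable AEs". Two reductions are permitted. Permanent discontinuation is tied to recurrence: "If unacceptable AEs recur despite 2 dose reductions, the study treatment will be permanently discontinued and post-treatment follow-up ensues". An exception for patients with clinical benefit, after discussion with the sponsor, follows directly on that sentence.
- **Section 2.6.8, Table 1.** Dosing restarts if the event resolves to Grade 1 or lower within 2 weeks. Otherwise: "If recovery takes >2 weeks, discontinue study drug". That sentence appears in the uncomplicated hematological, complicated hematological and Grade 3 non-hematological rows. No row covers a treatment delay as such.

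**The concern.** Whether a patient is re-treated or taken off drug after a slow recovery from toxicity should not depend on which page the site consults. A site working from the synopsis would restart at a lower dose. A site working from Table 1 would stop. The study plans 25 to 35 sites in Japan and 10 to 15 in South Korea, so divergent practice is plausible, and the safety monitoring board would then be reviewing data generated under mixed rules.

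There is also a possible route to the primary analysis. The primary efficacy set is the per protocol set (PPS), and membership depends on what happens in Cycle 1.

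**Working it through.** No figure in the plan needs reproducing. The check is a comparison of texts.

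**1. The thresholds are the same.** 2 weeks × 7 days = 14 days. The delay item counts treatment delay and Table 1 counts recovery time. Because the item covers only delay caused by recovery, I treat them as the same event, apart from a day or so of scheduling.

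**2. Trace one case.** Take drug-related Grade 3 thrombocytopenia with no bleeding and no transfusion. This is in the uncomplicated row of Table 1 and is not on the unacceptable-toxicity list by itself. The drug is held and recovery takes 14 + 1 = 15 days.
- The delay now exceeds 14 days, so it is an unacceptable toxicity. The synopsis has dosing resume at a lower level.
- Recovery now exceeds 2 weeks. Table 1 has the drug discontinued.

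The same trace works for a complicated hematological event or a Grade 3 non-hematological event.

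**3. Let Table 1 govern.** The synopsis sentence ends by deferring to the protocol's guidelines, and Section 2.6.8 identifies those with Table 1. On that reading, any event in the three rows that meets the delay item has already met the stopping rule. The resumption that the synopsis attaches to the item could never occur for those events. No text sets an order of precedence.

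**4. Look for a provision that settles it.** Sections 2.4.1 and 2.6.6 only permit reduction or discontinuation. The recurrence rule in Section 2.6.8 concerns events after two reductions, not a first long hold. The clinical-benefit exception is attached to that rule, so it does not clearly reach this case.

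**5. Scope.** The conflict is confined to the three rows. A delay over 14 days from an event outside Table 1, for example Grade 2, has only the synopsis rule. In the text as available, it is unclear whether the 2-week sentence in the uncomplicated row covers neutropenia as well as thrombocytopenia.

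**6. Reach into the PPS.** Section 5.5.2 requires completion of Cycle 1 treatment, or discontinuation during Cycle 1 for clinical progression.
- A patient stopped in Cycle 1 for a long toxicity hold meets neither condition.
- For the 2-week limit to pass inside a 28-day cycle, the hold must start by about Day 28 − 14 = 14.
- Twice-weekly dosing over 4 weeks is 2 × 4 = 8 doses. A two-week hold loses about 2 × 2 = 4 of them, leaving about 4/8 = 50%. Section 2.12 sets its compliance line at 75%, though that line does not define PPS membership.
- Section 5.5.2 does not say whether such a patient, if restarted, has completed Cycle 1.

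So the rule applied may affect membership, but the text does not establish that the restarted patient would be counted.

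**The case against.** The best defence is that the synopsis is a summary and Section 2.6.8 is the operative text. The synopsis sentence is loose elsewhere too: its list includes other non-hematologic events of Grade 3 or higher, yet Table 1 and Section 2.6.9 stop the drug outright at Grade 4. Being on the list therefore cannot mean that every case resumes. This has force. It makes Table 1 the more natural reading, but it does not give the synopsis sentence a meaning for the delay item, and it leaves a reader of the synopsis alone with an unqualified instruction.

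A reader might also infer that Section 2.6.8 itself tells sites to resume after a long delay. It does not. It lists the event, refers to Table 1 and caps the number of reductions. The only explicit resumption wording is the synopsis sentence.

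A reader might further infer a loss of power or a shift in the response rate through the PPS. The documents do not support that. They give no frequency of long holds. Section 5.2 plans 50 to 60 enrolled to secure 40 evaluable, so a few losses need not take the PPS below 40. Any calculation would also have to assume that a patient held for more than 14 of 28 days still counts as completing Cycle 1.

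Finally, last patient in was planned for 3Q 2018 and this version is dated July 2021. On that schedule a clarification can no longer alter Cycle 1 conduct. It still matters for holds in later cycles and for how past holds are reported.

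**Conclusion.** The text is wrong as written. For events in three Table 1 rows, a recovery delay beyond 14 days is given two conflicting consequences, and the cross-reference to the guidelines softens the conflict without removing it. The conflict lies between one synopsis sentence, read with the toxicity list, and Table 1.

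Its importance is patient safety and uniform conduct across sites. An effect on PPS membership is possible for holds that begin in roughly the first half of Cycle 1, but its size cannot be stated from the documents, and no claim about power or response rate follows. The conclusion rests on treating delay due to recovery and recovery time as the same event.

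**What to change.** Reconcile the synopsis sentence, the unacceptable-toxicity list in both the synopsis and Section 2.6.8, and Table 1, so that a delay beyond 14 days has one stated consequence. The sponsor's clinicians must choose it; this review takes no position on which it should be. The same edit should make clear what applies to events that have no row in Table 1, and which events the 2-week sentence in the uncomplicated row covers.

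The cost is a few lines in a clarification letter or amendment.

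Optionally, add one listing of all holds over 14 days with the action taken and the patient's PPS status. Section 5.8 already promises dose intensity and reasons for departures from planned therapy, so this is a convenience. It would show which rule was applied to patients already treated.

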2.6.9 Management and Dosage Modifications for Non-Hematologic Adverse Events

In the event of Grade 3 non-hematologic AEs (excluding isolated abnormality of laboratory values not associated with clinical significance), study medication should be held. Appropriate treatment should be initiated. Patients will be closely monitored for recovery and managed following the Dose Adjustment Guideline. If the AEs recur despite two dose reductions as applicable, study treatment should be discontinued. Study treatment should be terminated if Grade 4 non-hematologic adverse events occur, following the Dose Adjustment Guideline.

2.7 Study Drug Administration

During this trial, patients will receive 40 mg HBI-8000 administered approximately 30 minutes after any regular meal as four 10 mg tablets BIW continuously. The dosing interval would be 3 to 4 days for a total of 80 mg over 7 days. At each visit when study medication is dispensed, the study site staff will contact the Interactive Web Response System (IWRS) before dispensing.

2.8 Packaging, Labelling and Storage

HBI-8000 10 mg tablets are packaged in high density polyethylene bottles closed with an induction seal and a child-resistant cap and contain a desiccant pack, and a cotton coil. Each bottle contains 26 tablets. Study drug labels will contain information to meet the applicable regulatory requirements. In case of discontinuation of treatment for any reason unused portion of the drug should be returned to hospital pharmacy.

Drug product will be stored at 2 to 8 ° C at hospital pharmacy until dispensing. After dispensing to patients, the drug will be transported to home in a cooler to maintain refrigerated condition. Once at home, the drug will be kept refrigerated until administration and out of reach of children all the time. The study drug shall be read as post-marketing clinical study drug in this protocol after the PTCL approval.

2.9 Patient Registration and Subject Number Assignment

Based on medical history, potentially eligible patients will be identified. After obtaining informed consent, the screening procedures will be performed and a 5-digit subject number will be assigned. The first 3 digits are the site number (provided by the sponsor to study sites). The last 2 digits are a sequential number within a study site. If a patient is assigned a subject number and later found unable to begin HBI-8000 administration, the patient will be replaced. A new subject number will be assigned to the replacement patient.

2.10 Concomitant Treatments

All concomitant medications, regardless of whether they are prohibited or not, received after signing informed consent must be recorded on the eCRF. Complete information on all concurrent medications (generic name of drugs, reason for use, dosage and duration of dosing, etc.) should be documented in the original records and in the eCRF.

Patients should consult their investigator prior to using medications other than the study drug, including over-the-counter medications and supplements.

2.10.1 Prohibited Medications and Therapy

The following drugs are prohibited.

- Drugs known to produce significant QT prolongation and ventricular dysrhythmias (see Section 9.6)

Prohibited from signing informed consent through the EoT assessment

- Anti-cancer therapy other than study medication

Prohibited during the study and within the following time intervals prior to the first dose of study drug.

- 4 weeks for anti-cancer chemotherapy
- 6 weeks for nitrosourea and mitomycin C
- 12 weeks for anti-cancer monoclonal antibody therapy

Corticosteroid prescribed for medical conditions other than lymphoma is not considered as an anti-cancer therapy for this study, for example: chronic obstructive pulmonary disease for allergy, topical steroids for rash.

Please note that patient use of any prohibited medication is considered a protocol violation. In the event of prohibited medication use, investigator should consult study medical monitor to define an appropriate course of action if needed.

2.10.2 Cautioned Medications

Because the anti-emetic drug Zofran (ondansetron) is well known to prolong QTc, it is prohibited on 2 occasions, Cycle 1 Day 1 and Cycle 2 Day 1 when QTc test is scheduled. Starting 24 hours before the QTc test until the QTc test is completed on the next day, patient must not take Zofran over a 2-day period. Although anti-emetics are rarely needed for HBI-8000, if anti-emetics must be used for other medical reason, alternative drug(s) should be used. If a 5-HT3 antagonist must be used to manage severe emesis refractory to other medications, dosing should be postponed until resolution of underlying medical condition.

In case it is medically necessary to co-administer drugs that could interfere with CYP3A4 activity, investigators should monitor for toxicities and follow the study drug dose modifications for toxicity per study protocol. Also, St. John's wort should be used with caution.

2.10.3 Permitted Medications

Use of supportive care for AEs is permitted. These treatments may include anti-emetics, antipyretics, antidiarrheal, anti-allergy agents, rash reliever, antihypertensive drugs, analgesics, antibiotics, hematopoietic growth factors and transfusion with blood products.

Sulfamethoxazole Trimethoprim use is permitted. However, when its side effects are observed, alternative antibiotics prophylaxis should be considered.

